#### **HIV-Related Criteria:**

10. Willingness to receive **HIV test results**
11. Willingness to discuss HIV infection risks and amenable to HIV risk reduction counseling.
12. Assessed by the clinic staff as being at **“low risk” for HIV infection** and committed to maintaining behavior consistent with low risk of HIV exposure through the last required protocol clinic visit (see [Appendix H](#))

#### **Laboratory Inclusion Values**

##### **Hemogram/Complete blood count (CBC)**

13. **Hemoglobin**  $\geq 11.0$  g/dL for volunteers who were assigned female sex at birth,  $\geq 12.0$  g/dL for volunteers who were assigned male sex at birth.
14. **White blood cell count** = 2,500 to 12,000 cells/mm^3
15. **Total lymphocyte count**  $\geq 800$  cells/mm^3
16. **Remaining differential** either within institutional normal range or with site physician approval
17. **Platelets** = 100,000 to 550,000/mm^3

##### **Chemistry**

18. **Chemistry panel:** alanine amino transferase (ALT) and aspartate aminotransferase (AST)  $< 1.25$  times the institutional upper limit of normal; creatinine  $\leq$  institutional upper limit of normal.

##### **Virology**

19. **Negative HIV-1 and -2 blood test:** volunteers must have a negative FDA-approved enzyme immunoassay (EIA) within 56 days prior to enrollment.

20. **Negative Hepatitis B surface antigen (HBsAg)** within 56 days prior to enrollment
21. **Negative anti-Hepatitis C virus antibodies (anti-HCV)**, or negative HCV polymerase chain reaction (PCR) if the anti-HCV is positive within 56 days prior to enrollment

### Urine

#### 22. **Normal urine by urinalysis:**

- Negative urine glucose, and
- Negative or trace urine protein, and
- Red blood cell (RBC) levels within institutional normal range, and
- No RBC casts

### **Reproductive Status**

23. **Volunteers who were assigned female sex at birth:** negative serum or urine beta human chorionic gonadotropin ( $\beta$ -HCG) pregnancy test in accordance with local regulatory requirements, performed prior to vaccination on the day of initial vaccination. Persons who are NOT of reproductive potential due to having undergone total hysterectomy or bilateral oophorectomy (verified by medical records), are not required to undergo pregnancy testing.

#### 24. **Reproductive status:** A volunteer who was assigned female sex at birth must:

- Agree to use effective contraception for sexual activity that could lead to pregnancy from at least 21 days prior to enrollment through the last required protocol clinic visit. Effective contraception is defined as using the following methods:
  - Condoms (male or female) with or without a spermicide,
  - Diaphragm or cervical cap with spermicide,
  - Intrauterine device (IUD),
  - Hormonal contraception, or
  - Any other contraceptive method approved by the HVTN 121 PSRT
  - Successful vasectomy in any partner assigned male sex at birth (considered successful if a volunteer reports that a male partner has [1] documentation of azoospermia by microscopy, or [2] a vasectomy more than 2 years ago with no resultant pregnancy despite sexual activity postvasectomy);

- Or not be of reproductive potential, such as having reached menopause (no menses for 1 year) or having undergone hysterectomy, bilateral oophorectomy, or tubal ligation;
  - Or be sexually abstinent.
25. **Volunteers who were assigned female sex at birth must also agree not to seek pregnancy through alternative methods**, such as artificial insemination or *in vitro* fertilization until after the last required protocol clinic visit

## 7.2 Exclusion criteria

### General

1. **Blood products** received within 120 days before first vaccination
2. **Investigational research agents** not used to treat SLE received within 30 days before first vaccination (additional exclusions may apply, see 13 below)
3. **Intent to participate in another study** of an investigational research agent or any other study that requires non-HVTN HIV antibody testing during the planned duration of the HVTN 121 study
4. **Pregnant or breastfeeding**
5. **Active duty and reserve US military personnel**

### **SLE status. The following criteria must be verified by a rheumatologist or designee**

6. **Currently with active lupus** as defined by a Systemic Lupus Erythematosus Disease Activity Index (100) (SELENA-SLEDAI) > 4 (106) (see [Appendix G](#)).
7. **Documented SLEDAI score of > 20 in medical record at any time** indicating severe activity (106), or evidence of moderate disease activity (SELENA-SLEDAI > 6) within the last six months, (see [Appendix G](#)).
8. **Has had a condition listed on the Systemic Lupus International Collaborating Clinics/American College of Rheumatology Damage Index (SLICC/ACR DI) (105)** or has had an increase in the SLICC/ACR DI score within the last 12 months other than cataracts, premature ovarian failure or diabetes mellitus with approval of the PSRT  
<http://www.clinexprheumatol.org/article.asp?a=2697>
9. A history of **central nervous system (CNS) disease**

10. **Thrombotic event within the past 12 months in association with confirmed antiphospholipid antibody**
11. **A history of renal disease** (SLE-related renal injury) confirmed by prior biopsy, active urine sediment, or proteinuria
12. **Prednisone dose** > 10 mg/day for more than 6 months within the past year
13. **Administration of anti-B-cell therapy** (rituximab or belimumab) or any investigational research agents used to treat SLE within the preceding 2 years
14. **Administration of cyclophosphamide** within the preceding year; or administration of mycophenolate mofetil within the last 6 months; or administration of methotrexate, leflunomide, or azathioprine within the last 3 months
15. **Administration of any investigational immunosuppressant medication** within the last year
16. **Administration of other immunosuppressive medications** not listed above, with the exception of topical steroids, topical immunosuppressives (eg, cyclosporine, FK506), or ophthalmic immunosuppressives (eg, steroids, cyclosporine), within 6 months before first vaccination, unless approved by the HVTN 121 PSRT

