**Clinically significant medical conditions**

24. **Ongoing bleeding or hemorrhage** (excluding menstruation), or any subject on anticoagulant therapy
25. **Clinically significant medical condition**, physical examination findings, clinically significant abnormal laboratory results, or past medical history with clinically significant implications for current health, **other than SLE and its manifestations**. A clinically significant condition or process includes but is not limited to:
  - A process that would affect the immune response,
  - A process that would require medication that affects the immune response,
  - Any contraindication to repeated injections or blood draws,
  - A condition that requires active medical intervention or monitoring to avert grave danger to the volunteer's health or well-being during the study period,
  - A condition or process for which signs or symptoms could be confused with reactions to vaccine, or
  - Any condition specifically listed among the exclusion criteria below.
26. **Any medical, psychiatric, occupational, or other condition** that, in the judgment of the investigator, would interfere with, or serve as a contraindication to, protocol adherence, assessment of safety or reactogenicity, or a volunteer's ability to give informed consent
27. **Psychiatric condition that precludes compliance with the protocol**. Specifically excluded are persons with psychoses within the past 3 years, ongoing risk for suicide, or history of suicide attempt or gesture within the past 3 years.
28. **Current anti-tuberculosis (TB) prophylaxis or therapy**
29. **Asthma exclusion criteria:**

**Asthma** other than mild, well-controlled asthma. (Symptoms of asthma severity as defined in the most recent National Asthma Education and Prevention Program (NAEPP) Expert Panel report).

Exclude a volunteer who:

- Uses a short-acting rescue inhaler (typically a beta 2 agonist) daily, or
- Uses moderate/high dose inhaled corticosteroids, or
- In the past year has either of the following:
  - Greater than 1 exacerbation of symptoms treated with oral/parenteral corticosteroids;
  - Needed emergency care, urgent care, hospitalization, or intubation for asthma.

30. **Uncontrolled diabetes mellitus, Hb A1C > 7.0.** (not excluded: history of isolated gestational diabetes.)

31. **Uncontrolled hypertension:**

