# Appendix G SELENA-SLEDAI Instrument

## SELENA-SLEDAI Flare Composite

### SELENA-SLEDAI (Systemic Lupus Erythematosus Disease Activity Index) INSTRUMENT SCORE

Check box: if descriptor is present at the time of visit or in the preceding 10 days.

Wt	Check if Present	Descriptor	Definition
8		Seizure	Recent onset (last 10 days). Exclude metabolic, infectious or drug cause, or seizure due to past irreversible CNS damage.
8		Psychosis	Altered ability to function in normal activity due to severe disturbance in the perception of reality. Include hallucinations; incoherence; marked loose associations; impoverished thought content; marked illogical thinking; bizarre, disorganized or catatonic behavior. Exclude uremia and drug causes.
8		Organic brain syndrome	Altered mental function with impaired orientation, memory or other intellectual function, with rapid onset and fluctuating clinical features. Include clouding of consciousness with reduced capacity to focus, and inability to sustain attention to environment, plus at least 2 of the following: perceptual disturbance, incoherent speech, insomnia or daytime drowsiness, or increased or decreased psychomotor activity. Exclude metabolic, infectious or drug causes.
8		Visual disturbance	Retinal and eye changes of SLE. Include cytoid bodies, retinal hemorrhages, serous exudate or hemorrhages in the choroid, optic neuritis, scleritis or episcleritis. Exclude hypertension, infection or drug causes.
8		Cranial nerve disorder	New onset of sensory or motor neuropathy involving cranial nerves. Include vertigo due to lupus.
8		Lupus headache	Severe persistent headache: may be migrainous, but must be nonresponsive to narcotic analgesia.
8		CVA	New onset of cerebrovascular accident(s). Exclude arteriosclerosis or hypertensive causes.
8		Vasculitis	Ulceration, gangrene, tender finger nodules, periungual infarction, splinter hemorrhages, or biopsy or angiogram proof of vasculitis.
4		Arthritis	More than 2 joints with pain and signs of inflammation (i.e., tenderness, swelling or effusion).
4		Myositis	Proximal muscle aching/weakness, associated with elevated creatine phosphokinase/aldolase or electromyogram changes or a biopsy showing myositis.

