4		Urinary casts	Heme-granular or red blood cell casts.
4		Hematuria	>5 red blood cells/high power field. Exclude stone, infection or other cause.
4		Proteinuria	New onset or recent increase of more than 0.5 gm/24 hours.
4		Pyuria	>5 white blood cells/high power field. Exclude infection.
2		Rash	Ongoing inflammatory lupus rash.
2		Alopecia	Ongoing abnormal, patchy or diffuse loss of hair due to active lupus.
2		Mucosal ulcers	Ongoing oral or nasal ulcerations due to active lupus.
2		Pleurisy	Classic and severe pleuritic chest pain or pleural rub or effusion or new pleural thickening due to lupus.
2		Pericarditis	Classic and severe pericardial pain or rub or effusion, or electrocardiogram confirmation.
2		Low complement	Decrease in CH50, C3 or C4 below the lower limit of normal for testing laboratory.
2		Increased DNA binding	>25% binding by Farr assay or above normal range for testing laboratory.
1		Fever	>38°C. Exclude infectious cause.
1		Thrombocytopenia	<100,000 platelets/mm  .
1		Leukopenia	<3,000 white blood cells/mm  . Exclude drug causes.

_____ TOTAL SCORE (Sum of weights next to descriptors marked present)
			

Categorize as "Mild or Moderate" Flare or "Severe" Flare if the patient has at least one of the listed criteria in that category:	
Mild or Moderate Flare 	Severe Flare 
 Increase in SLEDAI $\geq$ 3 points, but not > 12	 Increase to a SLEDAI > 12

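### Exclusion criterion 12 limits prolonged prednisone use but not current dose: a volunteer above 10 mg/day for SLE at Day 0, with 6 months or less above it, meets no dose-based exclusion

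*Combined protocol and SAP*

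**What the plan says.** The trial is for people whose SLE is quiescent when they enroll (Section 3, Participants), and primary objective 2 refers to stable disease (Section 5.1). Section 4.1.2 concludes from the vaccination literature that recruiting people with low baseline activity is important.

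The SLE-status criteria in Section 7.2 put this into effect under the heading "The following criteria must be verified by a rheumatologist or designee":

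- Criterion 6 excludes a current SELENA-SLEDAI above 4.
- Criterion 7 excludes, among other things, "evidence of moderate disease activity (SELENA-SLEDAI > 6) within the last six months".
- Criterion 12 excludes a prednisone dose "> 10 mg/day for more than 6 months within the past year".
- Criterion 14 excludes methotrexate, leflunomide or azathioprine in the last 3 months and mycophenolate in the last 6, with no dose threshold.
- Criterion 16 excludes, for 6 months and unless the PSRT approves, immunosuppressives "not listed above, with the exception of topical steroids, topical immunosuppressives" and ophthalmic ones.

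Criterion 25 excludes clinically significant conditions, including those needing medication that affects immunity, but only conditions "other than SLE and its manifestations". Criterion 26 and the opening of Section 7 leave room for investigator judgment.

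Appendix G has two parts: a weighted activity score, and a list that classes a flare as mild or moderate, or as severe, "if the patient has at least one of the listed criteria in that category".

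**The concern.** Criterion 12 is the only eligibility rule that names prednisone, and it looks backward at cumulative exposure. It does not ask what the volunteer is taking at first vaccination. Someone placed on a substantial dose a few months ago, whose disease has settled on it, can enter without a dose-based exclusion and without PSRT review. For the same person, any recent azathioprine or methotrexate would be disqualifying.

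A low SELENA-SLEDAI in that setting may reflect the drug rather than quiescent disease. If activity returns as the dose is tapered, a confirmed moderate or severe flare counts, whatever its cause, toward the three that pause the trial at once (Table 11-8). With one arm and no concurrent control, such a flare is hard to tell from a vaccine effect. The stake is the safety assessment and whether the entry rules describe the intended population.

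**Working it through.** The plan states no figure on this point, so the check is mainly a reading of the rules against each other.

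**1. Criterion 12 as a conjunction.** Exclusion needs a dose above 10 mg/day and more than 6 months at that level within the past year.

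| Volunteer at Day 0 | Time above 10 mg/day in past year | Excluded by criterion 12? |
|---|---|---|
| 20 mg/day | 3 months | No (3 is not more than 6) |
| 40 mg/day | exactly 6 months | No (6 is not more than 6) |
| 15 mg/day | 7 months | Yes |

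**2. Does another rule cap the dose?**

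- Criterion 16 reaches only drugs not already listed, and prednisone is listed in criterion 12.
- Criterion 25 exempts SLE.
- Criterion 29 limits inhaled corticosteroids, for asthma only.
- Inclusion criterion 4 requires hydroxychloroquine and sets no steroid ceiling.
- Sections 7.3.1 and 7.3.3 contain no steroid-dose rule for delaying or stopping vaccination.
- The prednisone doses in Table 11-8 and Appendix G grade flares on study; they are not entry limits.

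**3. Do the activity limits do the same work?** The Appendix G score has no medication item. Treated activity can have scored 6 or less:

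- Arthritis ("More than 2 joints with pain and signs of inflammation") has weight 4 and rash ("Ongoing inflammatory lupus rash") has weight 2. 4 + 2 = 6, which is not above 6, so criterion 7 is not met.
- Thrombocytopenia has weight 1.
- Hemolytic anemia has no score item; it appears only in the severe-flare list.

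If treatment has since brought the score to 4 or less and blood counts inside the inclusion limits, criteria 6 and 7 and the laboratory limits are all satisfied.

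**4. How recent is the dose rise?** If total time above 10 mg/day in the past year is at most 6 months and use is ongoing, the current unbroken stretch is also at most 6 months. The last rise through 10 mg/day therefore came within 6 months of Day 0. Under Appendix G a prednisone increase alone is enough for a flare: mild or moderate if not above 0.5 mg/kg/day, severe if above. Entry applies the score but not that list.

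**5. Where the severe-flare dose begins.** Dose = 0.5 × weight in kg. The lower weight limit is 110 lb (inclusion criterion 2): 110 × 0.4536 = 49.9 kg. The other weights are assumptions.

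| Weight (kg) | 0.5 mg/kg/day |
|---|---|
| 49.9 | 24.9 mg/day |
| 60 | 30 mg/day |
| 80 | 40 mg/day |
| 100 | 50 mg/day |

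Criterion 12 excludes none of these doses when time above 10 mg/day is 6 months or less. The table converts units; it does not predict who would enroll.

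**6. Size per participant.** 1/16 = 6.25% of the cohort.

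**The case against.** The strongest reply is that meeting no dose-based exclusion is far from being enrolled. Criterion 26 excludes any condition that the investigator judges would interfere with assessing safety, and unlike criterion 25 it has no SLE exemption. Section 7 says some volunteers may be unsuitable even when every criterion is met. The arthritis-plus-rash example sits exactly at the limit: low complement or raised anti-dsDNA adds 2 points, making 8, and criterion 7 then excludes. This stands, and it is why the affected group is narrow. But these safeguards set no dose threshold, so sites may apply them differently, and the rheumatologist is asked to verify listed criteria, none of which caps current dose.

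Second, the protocol defines activity by score, and quiescence on treatment is intended, since hydroxychloroquine is mandatory. That is a coherent choice in general. It does not explain why current prednisone at any dose needs no review when other immunosuppressives are excluded or sent to the PSRT, and the documents give no reason for leaving current dose open.

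Third, the exception for topical steroids in criterion 16 might suggest that systemic steroids were meant to be covered. On that reading any prednisone within 6 months would need PSRT approval, and the 10 mg/day allowance in criterion 12 would have little purpose. Two possible readings are themselves a reason to clarify.

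Fourth, the harm is assumed and partly managed. The documents give no rate of flare on taper. Section 6.1.1.2 already projects 6.1 flares in a year, not split by severity, so the added effect of one participant on the three-flare rule is unclear. A pause can be lifted after review, the PSRT includes a rheumatologist, SLE status is assessed before each vaccination, and Section 7.3.3 stops dosing after a related severe flare or one a rheumatologist judges serious enough. All of this stands and lowers the weight of the point.

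**Conclusion.** The gap is real on the text: current prednisone above 10 mg/day for SLE, with 6 months or less above that dose in the past year, meets no dose-based exclusion and triggers no PSRT review. How many people it would admit is unknown and may be zero; each is 6.25% of the cohort. The safety consequence rests on two assumptions that the documents do not quantify: that a low score on a recently raised dose reflects suppression, and that disease returns on taper.

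Three stronger readings are tempting and are not supported. A reader might infer that volunteers on 25 to 50 mg/day will be enrolled; nothing in the documents suggests that any would pass the activity limits, laboratory limits and investigator judgment. A reader might infer that the gap will bring about a trial pause; that needs three confirmed moderate or severe flares, and the documents give no rate for this group. A reader might also infer damage to the broadly neutralizing antibody endpoint; the case does not rest on that, and the documents give no effect size for prednisone at these doses.

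This is a cheap improvement to safety and coherence at entry, of low severity.

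**What to change.** Keep the existing wording of criterion 12 unchanged as 12a, with no exception. Add:

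> 12b. Systemic corticosteroid dose > 10 mg/day prednisone or equivalent at enrollment or at any time in the 28 days before first vaccination, unless approved by the HVTN 121 PSRT.

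Also state that criterion 16 still applies to systemic corticosteroids other than prednisone. Otherwise naming them in 12b would take them out of criterion 16.

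The threshold is the protocol's own, and 28 days matches the eligibility window in Section 7. The look-back matters: a test of the Day 0 dose alone would pass someone tapered from 40 to 10 mg/day just before enrollment. Both unexcluded cases in the first table would then need PSRT approval.

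Limits: 12b will not catch a rise that stays at or below 10 mg/day (5 to 10 mg/day, for example), or a taper to 10 mg/day or less completed more than 28 days earlier.

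Cost: one added criterion and a slightly smaller recruitment pool. No new data collection should be needed, because medical records and concomitant medications are reviewed at screening (Section 9.2) and medications again before each vaccination (Section 9.3).

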### **Vaccines and other Injections**

17. **HIV vaccine(s)** received in a prior HIV vaccine trial. For volunteers who have received control/placebo in an HIV vaccine trial, the HVTN 121 PSRT will determine eligibility on a case-by-case basis.
18. **Non-HIV experimental vaccine(s) received within the last 5 years** in a prior vaccine trial. Exceptions may be made by the HVTN 121 PSRT for vaccines that have subsequently undergone licensure by the FDA. For volunteers who have received control/placebo in an experimental vaccine trial, the HVTN 121 PSRT will determine eligibility on a case-by-case basis. For volunteers who have received an experimental vaccine(s) greater than 5 years ago, eligibility for enrollment will be determined by the HVTN 121 PSRT on a case-by-case basis.
19. **Vaccines** received within 30 days before first study vaccination or scheduled within 30 days after injection (eg, influenza, tetanus, pneumococcal, Hepatitis A or B, measles, mumps, and rubella [MMR]; oral polio vaccine [OPV]; varicella; yellow fever)
20. **Allergy treatment with antigen injections** within 30 days before first vaccination or that are scheduled within 14 days after first vaccination

### **Immune System**

21. **Serious adverse reactions to vaccines or to vaccine components** (such as yeast protein, amorphous aluminum hydroxyphosphate sulfate, L-histidine, polysorbate 80, sodium borate), including history of anaphylaxis and related symptoms such as hives, respiratory difficulty, angioedema, and/or abdominal pain. (Not excluded from participation: a volunteer who had a nonanaphylactic adverse reaction to pertussis vaccine as a child.)
22. **Immunoglobulin** received within 60 days before first vaccination
23. **Immunodeficiency**, such as common variable immunodeficiency

**Clinically significant medical conditions**

24. **Ongoing bleeding or hemorrhage** (excluding menstruation), or any subject on anticoagulant therapy
25. **Clinically significant medical condition**, physical examination findings, clinically significant abnormal laboratory results, or past medical history with clinically significant implications for current health, **other than SLE and its manifestations**. A clinically significant condition or process includes but is not limited to:
  - A process that would affect the immune response,
  - A process that would require medication that affects the immune response,
  - Any contraindication to repeated injections or blood draws,
  - A condition that requires active medical intervention or monitoring to avert grave danger to the volunteer's health or well-being during the study period,
  - A condition or process for which signs or symptoms could be confused with reactions to vaccine, or
  - Any condition specifically listed among the exclusion criteria below.
26. **Any medical, psychiatric, occupational, or other condition** that, in the judgment of the investigator, would interfere with, or serve as a contraindication to, protocol adherence, assessment of safety or reactogenicity, or a volunteer's ability to give informed consent
27. **Psychiatric condition that precludes compliance with the protocol**. Specifically excluded are persons with psychoses within the past 3 years, ongoing risk for suicide, or history of suicide attempt or gesture within the past 3 years.
28. **Current anti-tuberculosis (TB) prophylaxis or therapy**
29. **Asthma exclusion criteria:**

**Asthma** other than mild, well-controlled asthma. (Symptoms of asthma severity as defined in the most recent National Asthma Education and Prevention Program (NAEPP) Expert Panel report).

Exclude a volunteer who:

- Uses a short-acting rescue inhaler (typically a beta 2 agonist) daily, or
- Uses moderate/high dose inhaled corticosteroids, or
- In the past year has either of the following:
  - Greater than 1 exacerbation of symptoms treated with oral/parenteral corticosteroids;
  - Needed emergency care, urgent care, hospitalization, or intubation for asthma.

30. **Uncontrolled diabetes mellitus, Hb A1C > 7.0.** (not excluded: history of isolated gestational diabetes.)

31. **Uncontrolled hypertension:**

- If a person has a history of hypertension, or is found to have elevated blood pressure or hypertension during screening, exclude for blood pressure that is not well controlled. Well-controlled blood pressure is defined as consistently  $\leq 140$  mm Hg systolic and  $\leq 90$  mm Hg diastolic, with only isolated, brief instances of higher readings, which must be  $\leq 150$  mm Hg systolic and  $\leq 100$  mm Hg diastolic. For these volunteers, blood pressure must be  $\leq 140$  mm Hg systolic and  $\leq 90$  mm Hg diastolic at enrollment.
- If a person has NOT been found to have elevated blood pressure or hypertension during screening or previously, exclude for systolic blood pressure  $\geq 150$  mm Hg at enrollment or diastolic blood pressure  $\geq 100$  mm Hg at enrollment.

32. **Bleeding disorder** diagnosed by a doctor (eg, factor deficiency, coagulopathy, or platelet disorder requiring special precautions)

33. **Malignancy** (not excluded from participation: Volunteer who has had malignancy excised surgically and who, in the investigator's estimation, has a reasonable assurance of sustained cure, or who is unlikely to experience recurrence of malignancy during the period of the study)

34. **Seizure disorder:** History of seizure(s) within past three years. Also exclude if volunteer has used medications in order to prevent or treat seizure(s) at any time within the past 3 years.

35. **Asplenia**: any condition resulting in the absence of a functional spleen (not excluded: splenectomy for splenic trauma)
36. History of hereditary **angioedema**, acquired angioedema, or idiopathic angioedema.

